Before the consent is signed, the decision-making capacity tool will be administered. This tool asks the Veteran to explain, in general, what the purpose of the study is and what is expected, in general from the participant. If the Veteran fails to demonstrate an understanding, they will not be eligible for the study.

When the signed informed consent forms are completed, a note will be made in the Hines VA EMR, and the original consent will be kept in a locked cabinet in a locked research office behind swipe-access doors in [name] of Hines VA. Additionally, a copy will be provided to the participant.

During the same visit for informed consent, participants will be asked to complete additional screening and neuropsychological testing. Table 1 lists all standardized tests. Completion of consenting and screening is expected to take approximately 3 hours.

Phase 1 In Person-Screening

Screening for Depression: Participants will be screened with the Beck Depression Index-II. Those scoring between 29- 63 will be withdrawn from the study as this indicates severe depression.

Screening for Anxiety: Participants will be screened with the Beck Anxiety Scale. Those scoring 12 or greater will be withdrawn from the study as this indicates severe anxiety.

Screening for Apathy: Participants will be screened with the Starkstein Apathy Scale. Those scoring 14 or greater will be withdrawn from the study as this indicates severe apathy.

Screening for global cognitive function: First, participants will be screened with the MoCA (e.g., level 1 screening). Those scoring below 21 will be withdrawn from the study as this indicated dementia.

Phase 2 In-Person Screening

Screening for PD-MCI: The following tests for 5 cognitive domains will be used. Executive function: Trail making test, Action Fluency test, Wisconsin Card Sorting Test. Memory: Hopkins Verbal Learning Test-Revised, Brief Visuospatial Memory Test-Revised. Visuospatial: Judgment of Line Orientation, Hooper Visual Organization Test. Language: Similarities, Boston Naming Test. Attention/working memory: Letter number sequencing, Stroop color word test

Additional tests and questionnaires: Theories of Cognitive Abilities, Need for Cognition Scale, Memory for

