Intentions Test and Modified Fatigue Impact Scale. A questionnaire will also be administered to obtain demographic information (age, gender, ethnicity, race, and education level), service-related information (active duty or reserves and period of service time, and Parkinson's disease-related history (year of diagnosis, number of years on Parkinson's medication and side of motor symptom onset), and current general computer use and use of commercially available cognitive training tools.

Table 1: Standardized Assessment Tools for In-Person Screening Visit		
Assessment Name	Construct measure	Time to complete (min)
Phase One of In-Person Screening		
Beck Depression Inventory-II	Depression	10
Montreal Cognitive Assessment	Global cognitive function	10
Beck Anxiety Inventory	Anxiety	10
Starkstein Apathy Scale	Apathy	5
		Total time: 35 minutes
Phase Two of In-Person Screening		
Letter number sequencing	Attention/working memory	5
Stroop color word test		10
Wisconsin Card Sorting Test	Executive function	15
Trail making test		5
Action Fluency Test		1
Hopkins Verbal Learning Test-Revised	Memory	10
Brief Visuospatial Memory Test-Revised		10
Judgment of Line Orientation short version	Visuospatial	10
Hooper Visual Organization Test		15
Similarities test	Language	10
Boston Naming Test Short form		5
Theories of Cognitive Abilities	Expectation of cognitive change	3
Need for Cognition Scale	Enjoyment of cognitively challenging tasks	5
The Memory for Intentions Test	Prospective memory	15
Modified Fatigue Impact Scale	Fatigue	5
		Total Time: 124 minutes

Table 2. Guidelines from the Movement Disorder Society Task Force on Defining & Assessing MCI¹⁰	
Assessment:	
Level 1	Allows for diagnosis of possible PD-MCI using either a test to assess global cognitive function (i.e., the MoCA) or a limited battery of neuropsychological tests. Based on MoCA total scores, 26 or higher indicates PD-N, 21-25 indicates PD-MCI and less than 21 indicates PD-D ^{41,42} .
Level 2	Allows for diagnosis and subtyping of PD-MCI using a full battery of neuropsychological tests which should include at least two tests in each of the five domains most affected in PD.
Definition of impairment: Using neuropsychological tests and appropriate normative data; impairment is defined as 1 standard deviation below normative mean in 2 tests in the same domain or any two tests in different domains.	

Phase 3: Baseline data collection

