Repeated measures/study outcomes are included in a standardized battery of test that will be repeated at baseline, endpoint and follow-up. The battery is expected to take approximately 130 minutes to complete.

Tests administered during screening (e.g., the BDI-II, MoCA, BAI, and HVLT, Memory for Intentions Test, and Modified Fatigue Impact Scale) will not be replicated at baseline, but are included in Table 3 below to indicate it is a repeated measure.

Table 3: Repeated Measures Assessment Tools used in the RCT			
Assessment Name (Abbreviation)	Outcome	Construct measure	Time to complete (min)
NIH-EXAMINER components:	1° (composite score of 7 tests listed below)	Executive function	29 total
Dot counting	2°	Working Memory	7
1-back			5
2-back			5
Flanker	2°	Cognitive Control	5
Set Shifting			5
Letter	2°	Verbal Fluency	1
Category			1
Hopkins Verbal Learning Test-Revised (HVLT)	2°	Memory	10
Symbol Digit Modalities Test (SDMT)	2°	Processing speed	5
The Memory for Intentions Test (MIST)	2°	Prospective memory	15
Monetary-Choice Questionnaire	2°	impulsivity	10
Parkinson's Disease-Cognitive Functional Rating Scale (PD-CFRS)	2°	Real-life function	5
The Activity Measure for Post-Acute Care™ (AM-PAC™) –Applied Cognition questionnaire	2°	Real-life function	10
Timed instrumental activities of daily living (iADL)	2°	Real-life function	15
Beck Depression Inventory-II	2°	Depression	10
Beck Anxiety Inventory	2°	Anxiety	10
Starkstein Apathy Scale	2°	Apathy	5
Montreal Cognitive Assessment	2°	Global Cognition	10
Epworth Sleepiness Scale	2°	Sleepiness	5
Modified Fatigue Impact Scale	2°	Fatigue	5
			Total Time: 144 minutes

Phase 4: Intervention

Participants will be randomized to one of three groups: CCT+PRIIS (n=15), CCT+PRIIS control (n=15) or CCT control +PRIIS control (n=15) and issued a VA iPad to take home and complete the study intervention.

Participants and researchers who are administering and scoring outcome measures will be blinded to group assignment. Effectiveness of blinding will be evaluated by using data collected from mid-point and endpoint questionnaires that assess perception of training intervention⁶⁹. The PI will oversee the RCT and coordinate research procedures and thus will not be blinded to treatment assignments. [name], who will be blinded to group assignments, will coordinate sensitive aspects of the study that require blinding.

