5.0 Data Analysis

All test administrators will undergo the same training. Data will be cleaned and tested for normality (if normality tests fail, appropriate transformations will be made), and proper missing data imputation techniques will be used. Test for multicollinearity will be made. The 3 treatment groups will be characterized using descriptive statistics for demographic factors, disease-related variables, and medication use. Groups will be examined for comparability according to the descriptive variables using ANCOVA and mixed-effects model with random subject effects. For ANCOVA, type I error rate ($\alpha=0.05$) will be adjusted for multiple comparisons using Bonferroni corrections.

Neuropsychological Data Analytical Approaches. For Aims 2 and 3, data will be analyzed using a two-level longitudinal mixed effects model with random subject effects to incorporate correlation of measurements nested within the same subject. Covariates will include medication dose, anxiety, apathy, and depression level. Parameters will be estimated using measurements from baseline, endpoint, and follow-up. The group by time interaction parameter will be used to examine the difference of the trends between the three groups. Significance of this parameter will indicate that treatment is efficacious in terms of EF over time when adjusted by covariates. To assess immediate effects of CCT, an experiment group contrast will be formed using test score means at baseline and endpoint and a control group contrast will be made with those same types of means. To assess sustainability of CCT effects, contrasts using means of test scores at endpoint and follow-up will be made for each group. Estimates of variance components from mixed-model analysis will be used to calculate test statistics. Data analysis will be performed using SAS 9.3 Proc Mixed. This modeling process will be reported for each outcome of interest in Aims 2 and 3. Potential moderators of the effects of the CCT will be explored through Pearson correlations and regression analyses. Factors include, age, age at PD onset, disease duration, MoCA score, depression, anxiety, apathy, L-dopa equivalent dose, PD-MCI subtype diagnosis,

scores on training perception, prior computer use and cognitive training. Co-morbidities and medications will be considered as confounders.

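### Screening scores that decide entry also serve as baseline for the same secondary outcomes, so within-group change on those scales is expected to include regression towards the unselected mean

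*Combined protocol and SAP*

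**What the plan says.** **Entry.** The in-person screening part of Section 1.0 applies four cut-offs.
- BDI-II: "Those scoring between 29- 63 will be withdrawn from the study as this indicates severe depression".
- BAI: "Those scoring 12 or greater will be withdrawn from the study as this indicates severe anxiety".
- Starkstein Apathy Scale: "Those scoring 14 or greater will be withdrawn from the study as this indicates severe apathy".
- MoCA: "Those scoring below 21 will be withdrawn from the study as this indicated dementia".

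MCI status then comes from the Level 2 battery, in which HVLT-R is one of two memory tests. In Table 2, "impairment is defined as 1 standard deviation below normative mean in 2 tests in the same domain or any two tests in different domains".

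**Baseline.** Phase 3 of Section 1.0 says of the screening tests (its examples include BAI, BDI-II, HVLT and MoCA) that they "will not be replicated at baseline, but are included in Table 3 below to indicate it is a repeated measure". The same table lists BDI-II, BAI, Starkstein, MoCA and HVLT as secondary outcomes measured at baseline, endpoint and follow-up. The Starkstein scale is given at screening, but the sentence on carried-over tests offers only examples and does not name it, so its status is open.

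**Analysis.** Section 5.0 judges efficacy by the group-by-time interaction. For immediate effects of training it adds that "an experiment group contrast will be formed using test score means at baseline and endpoint", with a matching contrast for the control group. It does not mention that some baselines are the scores used for selection.

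**The concern.** When one measurement both admits a participant and serves as the pre-treatment value, the pre-treatment distribution is cut off at the entry threshold and later measurements are not. Part of what put a person on the eligible side is transient variation that will not recur. The expected change is then non-zero and in a known direction even if nothing happens to the patient.

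At stake is how change within an arm is read. A rise in anxiety, or a fall in MoCA, in the training arm could be taken as harm or could hide a small gain. HVLT works the other way: entry favours low scores, so it is expected to rise, which could look like benefit. Section 3.0 says these pilot data will support a larger grant proposal, where an arm's own before-and-after change may well be cited.

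**Working it through.** **1. Does the screening score really stand as baseline?** The Table 3 times sum to the stated 144 minutes. The six named screening tests take 10 (BDI-II) + 10 (MoCA) + 10 (BAI) + 10 (HVLT) + 15 (Memory for Intentions) + 5 (Modified Fatigue Impact) = 60. This leaves 144 − 60 = 84 minutes, in line with the roughly 90 minutes that Section 2.0 gives for the baseline visit. The carry-over is what the plan intends.

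**2. Model.** The documents give no mean, SD, retest correlation or share removed for any scale, so there is no figure of the plan's own to reproduce and these inputs are assumptions. Take standardised normal scores, retest correlation ρ, stable true scores, no treatment effect, and a fraction p removed by an upper cut-off at z, where Φ(z) = 1 − p. Then:
- expected baseline = −λ, with λ = φ(z)/(1 − p);
- expected endpoint = −ρλ;
- drift = (1 − ρ)λ.

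For MoCA the signs reverse.

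**3. Drift in population SD.**

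| Removed | λ | ρ = 0.6 | ρ = 0.7 | ρ = 0.8 |
|---|---|---|---|---|
| 2% | 0.049 | 0.02 | 0.01 | 0.01 |
| 5% | 0.109 | 0.04 | 0.03 | 0.02 |
| 20% | 0.350 | 0.14 | 0.11 | 0.07 |
| 30% | 0.497 | 0.20 | 0.15 | 0.10 |
| 50% | 0.798 | 0.32 | 0.24 | 0.16 |

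The share of entrants beyond the cut-off at retest, with no true change, is 9% to 30% for 20-50% removed and 1% to 4% for 2-5% removed.

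**4. Effect on a within-arm test.** Take p = 0.30 and ρ = 0.7.
- Drift = 0.3 × 0.497 = 0.149.
- Variance of the truncated baseline = 1 − zλ − λ² = 1 − 0.524 × 0.497 − 0.497² = 0.493.
- SD of change = √[(1 − ρ)² × 0.493 + 1 − ρ²] = √(0.044 + 0.510) = 0.745.
- Noncentrality for n = 15 = (0.149/0.745) × √15 = 0.77.
- A two-sided 5% paired t test then rejects 11.2% of the time, and 15.6% of entrants lie beyond the cut-off at retest.

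At 2-5% removed, the rejection rate is 5.0% to 5.4%.

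**5. In scale points.** These use assumed population means and SDs, ρ from 0.6 to 0.9, and continuity-corrected cut-offs.

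| Scale | Assumed mean; SD | Expected drift |
|---|---|---|
| BAI | 8-14; 7-9 | +0.4 to +3.5 |
| Apathy, if carried over | 10-15; 5-6 | +0.2 to +2.3 |
| BDI-II | 10-18; 7-9 | +0.01 to +0.8 |
| MoCA | 22-26; 3-4 | −0.02 to −0.9 |

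No arm mean crosses its cut-off in these scenarios. For example, with BAI mean 12, SD 9 and ρ = 0.75, the entrants' mean is 4.50 and the expected endpoint is 12 + 0.75 × (4.50 − 12) = 6.4, against a cut-off of 12.

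**6. Between arms.** Simulation of selected scenarios (4,000 trials each, 15 per arm, no effect) gave within-arm rejection of 11-40% for BAI, 17% for apathy, 7-17% for MoCA and 5% for BDI-II. Tests comparing change between arms rejected 4-6% of the time, and the mean difference between arms was about zero.

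**7. HVLT.** The direction is upward, because the MCI rule favours low scores. The size is not computed: the rule combines eleven tests, and the documents do not say how often HVLT decides entry.

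**The case against.** The strongest reply is that the plan does not rest on a single arm's change. Efficacy is defined by the group-by-time interaction, and the control contrast sits beside the experimental one. Both carry the same expected drift, so a reader who compares them is not misled. The affected scales are secondary in a pilot of 45, and reusing screening scores spares tired patients. The modelling is promised for outcomes of interest in Aims 2 and 3, which the supplied text does not set out. Anxiety, apathy and depression also appear as covariates, so it is not certain that the contrasts will be run on them. All of this stands and limits the point. It does not remove it, because Table 3 calls these scales secondary outcomes and Section 5.0 forms a contrast for each group to assess training effects without any caution.

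A reader might infer more than the documents support:
- *That arm means return past the entry cut-offs.* They move only part of the way back; it is some individuals who cross. A mean reaches the cut-off only in an extreme case, such as BAI population mean 20, SD 9, ρ = 0.6 (endpoint 12.0, with only 17% of those screened passing).
- *That the trial will report Veterans becoming severe.* Section 5.0 plans no tabulation against the entry cut-offs, and no change test pooled over all 45.
- *That every scale is materially affected.* Where few are removed, as is plausible for BDI-II, drift is close to nil. Chart review has already excluded recorded severe depression, anxiety, apathy and dementia.
- *That scores will be seen to worsen.* Practice on a repeated MoCA, true change over 8 to 12 weeks, or noise at n = 15 could offset or reverse the drift.

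**Conclusion.** The point holds for within-group baseline-to-endpoint change on BDI-II, BAI, MoCA and HVLT, and on apathy if it is carried over. Expected drift depends on the share removed: 0.07 to 0.32 SD at 20-50%, most plausible for BAI and for apathy if carried over, and 0.01 to 0.04 SD at 2-5%, plausible for BDI-II. MoCA lies between, small to modest. At 30% removed and correlation 0.7, the within-arm error rate is about 11% rather than 5%.

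These sizes rest on assumed normality, which ignores floor and skew in BAI and BDI-II, and on assumed retest correlations and removal rates. The direction of the expected drift needs only imperfect retest correlation and stable true scores.

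The group-by-time test and other between-arm comparisons are not biased, because randomisation spreads the drift equally. Endpoint-to-follow-up contrasts do not use the screening score. The primary NIH-EXAMINER composite is not a screening test and is unaffected. This is a correction to how some secondary results are analysed and read; it does not threaten the trial's main comparison.

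**What to change.** In Section 5.0, for BDI-II, BAI, MoCA and HVLT (and apathy, if carried over), replace the separate experimental and control baseline-to-endpoint contrasts with the between-arm difference at endpoint and at follow-up, adjusted for the screening score of that scale. Add one sentence saying that, because the baseline value helped decide entry, change within an arm on these scales is not evidence of benefit or harm. In Phase 3, state whether the apathy score is carried over.

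This costs wording only. The downside is that these secondary scales will have no within-arm effect estimate.

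Repeating the scales at baseline would also remove the problem, provided that screening errors are independent of later ones, but it is a trade-off in burden. BDI-II, BAI and MoCA add 30 minutes: 84 + 30 = 114. That is inside the 130 minutes of Phase 3 but about 24 above the roughly 90 that Section 2.0 gives for baseline, where fatigue is already flagged. Adding HVLT brings it to 124. The analysis-only change does not need this.

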PRIIS active control will include verbal rehearsal. These participants will be instructed to recite their prospective memory task (complete weekly intervention assignments) at least three times a day and study them for 30 s. Everyone will be given a handout with strategy instructions as reference. Weekly calls will be made to participants to assess their progress with the prospective memory task of completing weekly intervention assignments. Barriers, facilitators, and resources will be noted and discussed.

The study team member designated as the cognitive coach will make weekly phone calls to the participant to assess compliance and help troubleshoot any difficulties with the assigned programs. During the call, the cognitive coach will help the participant assess their progress with the prospective memory task of completing weekly intervention assignments (and for PRIIS the other goals). Barriers, facilitators, and resources will be discussed.

At midpoint and endpoint (weeks 4 and 8 of the intervention), participant's perception of the training will be assessed, over the phone and by a study team member, with a short questionnaire that will include questions such as: Are the games enjoyable? Are the games challenging? Do you look forward to playing the games? Are you motivated to play the games? Do you think your cognition is improving because of the games? Answers will be rated on a Likert scale. All participants will be reassessed with the neuropsychological battery at endpoint and one month after endpoint. During the one month after endpoint, participants will not be contacted during the one month except to remind them of their appointment for the follow-up assessment.

Specific to the CCT intervention, several factors may contribute to non-compliance with program use. Several elements of flexibility will be incorporated in the treatment schedule to accommodate the challenges that Veterans with PD may encounter. First, the participant may require extra time to complete the program. Participants will be asked to engage in four 30-minute sessions per week for 8 weeks, which is 16 hours in total.

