Training progress and compliance will be automatically uploaded to a secure HIPAA-compliant server at Posit Science, and will be monitored weekly by the study staff. If participants have completed less than 12 of the 16 hours of total training, then they will be allowed up to 4 additional weeks to complete the intervention. To ensure a time-bounded study commitment, after a total of 12 weeks such participants will perform their post-assessment (completion) visit regardless of the number of sessions completed. Second, we expect that not all participants will complete four sessions every week. To accommodate this, during the weekly phone calls to participants, the study team will work with them to generate a feasible training schedule if they are finding it difficult to meet requirements. Third, there may be some cases in which a participant may wish to stop or minimize the use of the program going forward, while remaining in the study. Potential reasons for this

decision might be a change in health issues, family/personal issues or lack of interest in the intervention. However, the participant may want to meet their personal commitment to the basic scientific research of the study. In such cases, after a study team discussion with co-investigators, the participant will be permitted to cease using the program and be scheduled for a post-assessment (endpoint) visit at the appropriate time relative to the baseline assessment. If the participant completed at least 12 hours of training within 12 weeks, then a 1-month follow-up assessment will be scheduled. Fourth, some Veterans may not be able to complete the proposed training regimen in one sitting (i.e., 30 minutes) due to fatigue. To accommodate this issue, participants may choose to break the time into shorter segments, which are more easily manageable.

We will define “completers” of the intervention as those who completed at least 80% of the sessions.

Phase 5: Endpoint

Endpoint Behavioral Assessments:

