All participants will complete the assessments listed in Table 3 in a private room with trained research staff at Hines. A semi-structured interview will also be conducted by trained research staff. This interview will take approximately 30 minutes and discussion will focus around feasibility of participating in the study, perception of training for the 2 interventions, usefulness of the weekly cognitive coach calls, and guess at treatment group allocation. We will audiotape this part of the session. The option to consent to audiotaping is included in the veterans's consent form

Phase 6: Follow-up

Follow-up Behavioral Assessments:

One month after the last intervention session, all participants will complete the assessments listed in Table 3 in a private room with trained research staff at Hines.

Unblinding:

Participants will be unblinded after the last participant completes the study. A letter will be mailed to the Veterans.

Knowledgeable informants/caregivers

Knowledgeable informants/caregivers enrolled in the study will be administered the PD-CFRS. Data from the informant will be collected at baseline in person and, to reduce burden of data collection, end-point and follow-up surveys will be mailed to informants for completion. Filling out this form three times (along with an initial demographic form) are the only research procedures performed by the knowledgeable informants/caregivers.

COMPENSATION FOR PARTICIPATION IN RESEARCH ACTIVITIES

Veteran participants will be compensated \$120 for completing all research procedures in this study. Participants will receive \$30 after completing the 2-3 hour long diagnostic confirmation screen. Participants will receive \$30 after completing baseline neuropsychological assessments, \$30 after completing endpoint neuropsychological assessments and \$30 after completing follow-up neuropsychological assessments.

Payment Procedures if screening and/or assessments are completed Hines VA: they will be reimbursed \$30 direct deposit via electronic funds transfer (EFT).

Knowledgeable informants/caregivers will not receive compensation.

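### The plan conflicts on which Veterans get the 1-month follow-up (all, or among those who stop or cut back only those with 12 training hours) and on which event starts the month

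*Combined protocol and SAP*

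**What the plan says.** **Who is followed up.** Section 1.0, Phase 4 lists ways of accommodating difficulty with training. The third concerns Veterans who "wish to stop or minimize the use of the program going forward, while remaining in the study". They are to "be scheduled for a post-assessment (endpoint) visit at the appropriate time relative to the baseline assessment", and then: "If the participant completed at least 12 hours of training within 12 weeks, then a 1-month follow-up assessment will be scheduled". Section 2.0 (Computer cognitive training intervention) repeats this word for word.

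Two other statements carry no condition. Phase 4 also says: "All participants will be reassessed with the neuropsychological battery at endpoint and one month after endpoint". Phase 6 says: "One month after the last intervention session, all participants will complete the assessments listed in Table 3".

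For slow trainers still below 12 hours, Phase 4 requires only that "after a total of 12 weeks such participants will perform their post-assessment (completion) visit regardless of the number of sessions completed". It attaches no follow-up condition to them.

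**When.** The first unconditional statement counts the month from endpoint, the second from the final session. Phase 4 places endpoint at week 8 of the intervention.

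**Use of the data.** Section 5.0 says: "Parameters will be estimated using measurements from baseline, endpoint, and follow-up". It also assesses sustainability by contrasting endpoint and follow-up means in each group.

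**The concern.** No sentence says outright that a Veteran who stops below 12 hours gets no follow-up, but the condition has no other purpose. Staff therefore have two instructions on whom to schedule and two dates to schedule from.

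If the condition is applied, whether a follow-up score exists depends on training hours accumulated after randomisation. If hours are related to executive function, the Veterans seen at follow-up are a selected group, and the sustainability contrast compares a full endpoint sample with that group. Section 5.0 promises proper imputation without naming a method and does not address visits that were deliberately never scheduled.

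If the unconditional statements govern, no data are lost, but the conflict over the date remains. It matters for early stoppers, because their endpoint is timed from baseline and not from their last session.

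**Working it through.** The plan gives no figure to reproduce here beyond its training total: 4 sessions × 0.5 h × 8 weeks = 16 h. Twelve hours is 75% of that, reached at the end of week 6 at the planned 2 h a week.

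**1. Dates.** One month = 365.25/12/7 = 4.35 weeks. Two assumptions: endpoint is at week 8 for stoppers too (the plan says only that the time is set relative to baseline), and the last intervention session is the last computerised training session.

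| Last session | Month counted from endpoint | Month counted from last session |
|---|---|---|
| Week 8 | week 12.35 | week 12.35 |
| Week 6 | week 12.35: 4.35 weeks after endpoint, 6.35 after training | week 10.35: 2.35 weeks after endpoint |
| Week 2 | week 12.35: 10.35 weeks after training | week 6.35: 1.65 weeks before endpoint |

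The dates agree for anyone who trains up to endpoint. With the last-session anchor, follow-up falls due before endpoint for any stop before week 8 − 4.35 = 3.65.

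**2. Possible bias if the condition is applied.** All inputs except n = 15 per arm are assumptions:

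- 5-20% of an arm are low-hour stoppers (about 1-3 of 15).
- Hours correlate ρ = 0.3-0.5 with executive function at endpoint and follow-up.
- The correlation between any two visits is r = 0.6-0.8.
- The correlation of hours with the baseline score is k times the later one, with k = 0-1.

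When a proportion p is seen and hours are roughly normal, mean hours among those seen are raised by λ(p) = φ(z_p)/p SD. This is 0.109 at p = 0.95 and 0.350 at p = 0.80. A random-intercept model using baseline and endpoint scores removes part of the resulting shift and leaves the fraction 1 − (1+k)r/(1+r):

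- k = 0, r = 0.6: 0.63
- k = 1, r = 0.8: 0.11

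Resulting shifts in SD units:

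- Between arms, 5% versus 20% loss: (0.350 − 0.109) × ρ × fraction = 0.008 to 0.075. It is zero if loss is equal.
- Within an arm, endpoint to follow-up: 0.012 to 0.109 at 20% loss and 0.004 to 0.034 at 5%.

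The low ends need k = 1. With k = 0 the ranges are 0.040-0.075 between arms and 0.058-0.109 within an arm at 20% loss.

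**3. Against the standard errors.**

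- Two-arm difference at follow-up: √(2/15) = 0.365, so the largest shift is 0.075/0.365 = 0.21 SE.
- Endpoint-to-follow-up change in one arm: √(2(1−r)/15) = 0.231 (r = 0.6) and 0.163 (r = 0.8). The largest shifts at matched r are 0.109/0.231 = 0.47 SE and 0.097/0.163 = 0.60 SE.

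**4. Precision with 12 of 15 seen.** R² of follow-up on the two earlier visits is 2r²/(1+r) = 0.45 and 0.711.

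- Follow-up mean: the SE is multiplied by √((1−R²)/0.8 + R²) = 1.067 and 1.035.
- Change: variance = 2(1−r)/15 + (1−R²)(1/12 − 1/15), giving SEs of 0.250 and 0.177, a rise of 8.3% and 8.7%. At 5% loss the rise is about 2%.

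**The case against.** The strongest reply is that the 12-hour sentence is a specific exception, for one subgroup, to a general schedule, which is an ordinary way to read a protocol. That is a fair reading, but neither unconditional statement contains an exception or a cross-reference. On that reading the selective loss of follow-up data is real, and the conflict between the two dates remains.

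A second reply is that the effects are too small to matter in a pilot. The sizes are indeed small, and the illustration ignores the anxiety, apathy and depression covariates in section 5.0, which may absorb part of any selection. Nothing in the documents shows that loss would differ by arm.

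Two narrower points also stand. Stops before about week 3.7 fall below 12 hours at the planned pace, so follow-up falling due before endpoint arises only where the condition is not applied. If it is applied, the two dates differ by about two weeks at most at that pace. And the plan does not say that the prospective-memory strategy ends when computer training ends. However, the plan uses the word sessions for computer training, so reading the last session that way is natural.

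**Conclusion.** The concern holds. The plan states the follow-up population both with and without a training-hours condition and counts the month from two different events. This should be fixed, but the reason is contradictory instructions about an outcome visit, not demonstrated large bias. The size and direction of any bias cannot be found from the documents. Under the assumptions above it reaches at most about 0.2 SE between arms and 0.6 SE within an arm, with up to about a 9% rise in the SE of the sustainability change. The within-arm maximum needs 20% loss, ρ = 0.5 and k = 0. Assessments that were never scheduled cannot be recovered at analysis.

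**What to change.** - **Population.** Delete the 12-hour condition from section 1.0 (Phase 4) and section 2.0. Invite every randomised Veteran who has not withdrawn consent, slow trainers included, as the unconditional statements already provide, and analyse all in the arm to which they were randomised.
- **Date.** Use one anchor in Phases 4 and 6 that keeps follow-up after endpoint. One month after endpoint does this. It also fits the no-contact month in Phase 4 and the informant mailing, which is timed one month after the Veteran completes the trial.
- **Record.** Capture days from last session to follow-up for each Veteran and report them by arm.

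The cost is a wording amendment with its IRB review, one extra recorded date and a few visits. At 5-20% of 45 Veterans, that is 2.25 to 9 visits. At about three hours (section 2.0) and 30 dollars (section 1.0, Compensation) each, this comes to about 7 to 27 hours and 70 to 270 dollars. The endpoint anchor also gives up a constant interval since training: about 4.3 weeks for a planned completer, 6.3 for a stop at week 6 and 10.3 for a stop at week 2. The recorded interval makes this visible.
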